Appendix F Procedures at HVTN CRS: Infant

Visit:	011	02	03	04	05	06	07	08	09	10	11	12	13	14	Post
Day:		D0	D1	D14	D56	D70	D112	D126	D224	D238	D379	D393	D516	D743	
Week		W0		W2	W8	W10	W16	W18	W32	W34	W54	W56	W74	W106	
Month:		M0		M0.5	M2	M2.5	M4	M4.5	M8	M8.5	M12.5	M13	M17	M24.5	
Procedure	Scr.	VAC1			VAC2		VAC3		VAC4		VAC5				
Study procedures															
Medical history	X	_	_	_	_	_	_	_	_	_	_	_	_	_	_
Feeding history		X	X	X	X	X	X	X	X	X	X	X	X	X	_
Complete physical exam	X	_	_	_	_	_	_	_	_	_	_	_	_	X	_
Abbreviated physical exam	_	X	X	X	X	X	X	X	X	X	X	X	X	_	
Obtain demographics (for infant)	X	_	_	_		_		_	_	_	_	_	_		
Randomize	_	X	_	_	_	_	_	_	_	_	_	_	_	_	_
Concomitant medications	X	X	X	X	X	X	X	X	X	X	X	X	X	X	_
Intercurrent illness/adverse experience	_	X	X	X	X	X	X	X	X	X	X	X	X	X	_
HIV assessment	X	_		_	_		_	_			_	_	X	X	
Confirm HIV assessment results provided to mother	_	X	_	_	_	_	_	_	_	_	_	_	_	X	X
Vaccination procedures															
Vaccination	_	X	_	_	X	_	X	_	X	_	X	_	_	_	
Reactogenicity assessments ²	_	X	_	_	X	_	X	_	X	_	X	_	_	_	
Specimen collection ³	X	X	X	X	X	X	X	X	X	X	X	X	X	X	_
Poststudy															
Unblind participant	_													_	X

¹ Screening may occur over the course of several contacts/visits up to and including day 0 prior to vaccination.

² Reactogenicity assessments performed daily for at least 3 days postvaccination (see Section 9.7).

³ For specimen collection requirements, see Appendix D, Laboratory procedures- Infant.

Appendix G Procedures at HVTN CRS: Mother

Visit:	01^{1}	02	03	04	05	06	07	08	09	10	11	12	13	14	Post
Day:		D0	D1	D14	D56	D70	D112	D126	D224	D238	D379	D393	D516	D743	
Week:		W0		W2	W8	W10	W16	W18	W32	W34	W54	W56	W74	W106	
Month:		M0		M0.5	M2	M2.5	M4	M4.5	M8	M8.5	M12.5	M13	M17	M24.5	
Procedure	Scr.														
Study procedures															
Assessment of understanding	X	_	_	_	_	_	_	_	_	_	_	_	_	_	_
Complete Physical Exam	X														
Signed protocol consent	X	_	_	_	_	_	_	_	_	_	_	_	_	_	_
Medical history	X	_	_	_	_	_	_	_	_	_	_	_	_	_	_
Risk reduction counseling ²	X	X	X	X	X	X	X	X	X	X	X	X	X	X	_
Confirm eligibility	X	_	_	_	_	_	_	_	_	_	_	_	_	_	_
Obtain demographics (for mother)	X	_	_	_	_	_	_	_	_	_	_	_	_	_	_
Social impact assessment	_	X	X	X	X	X	X	X	X	X	X	X	X	X	_
Outside testing of baby questionnaire	_	_	_	_	_	_	_	_	_		_	_	_	X	_
Belief questionnaire	_	_		_	X		_	_	X	_	_	_	_	X	
Concomitant medications	X	X	X	X	X	X	X	X	X	X	X	X	X	X	_
Specimen Collection ³	X	X		_	_	X	_	X	_	X	_	X	_	_	_
Poststudy															
Provide unblinding information to mother	_	_	_	_	_	_	_	_		_		_	-	_	X

 $^{^{1}}$ Screening may occur over the course of several contacts/visits up to and including day 0. 2 Risk reduction counseling, see Section 9.6 and HVTN 135 SSP.

³ For specimen collection requirements, see Appendix E, Laboratory procedures- Mother.

Appendix H Adverse events of special interest

AEs of special interest (AESI) for this protocol include but are not limited to potential immune-mediated diseases; representative examples of AESI are listed below. Updates to AESI will be provided as an appendix to the *HVTN 135 Study Specific Procedures*.

Gastrointestinal disorders	Liver disorders	Metabolic diseases
 Celiac disease Crohn's disease Ulcerative colitis Ulcerative proctitis 	 Autoimmune cholangitis Autoimmune hepatitis Primary biliary cirrhosis Primary sclerosing cholangitis 	Addison's disease Autoimmune thyroiditis (including Hashimoto thyroiditis) Diabetes mellitus type I Grave's or Basedow's
Neuroinflammatory disorders	Musculoskeletal disorders	disease Skin disorders
Acute disseminated encephalomyelitis, including site specific variants (eg, non-infectious encephalitis, encephalomyelitis, myelitis, myelo radiculomyelitis, myelitis, myelo radiculomyelitis) Cranial nerve disorders, included paralyses/paresis (eg, Bell's palsy) Guillain-Barré syndrome, including Miller Fisher syndrome and other variants Immune-mediated peripheral neuropathies and plexopathies, including chronic inflammatory demyelinating polyneuropathy, multifocal motor neuropathy and polyneuropathies associated with monoclonal gammopathy Multiple sclerosis Narcolepsy Optic neuritis Transverse Myelitis	 Antisynthetase syndrome Dermatomyositis Juvenile chronic arthritis (including Still's disease) Mixed connective tissue disorder Polymyalgia rheumatic Polymyositis Psoriatic arthropathy Relapsing polychondritis Rheumatoid arthritis Scleroderma, including diffuse systemic form and CREST syndrome Spondyloarthritis, including ankylosing spondylitis, reactive arthritis (Reiter's Syndrome) and undifferentiated spondyloarthritis Systemic lupus erythematosus Systemic sclerosis 	Alopecia areata Autoimmune bullous skin diseases, including pemphigus, pemphigoid and dermatitis herpetiformis Cutaneous lupus erythematosus Erythema nodosum Morphoea Lichen planus Psoriasis Sweet's syndrome Vitiligo
Vasculitides	Other	s
Large vessels vasculitis including: giant cell arteritis such as Takayasu's arteritis and temporal arteritis Medium sized and/or small vessels vasculitis including: polyarteritis nodosa, Kawasaki's disease, microscopic polyangiitis, Wegener's granulomatosis, Churg-Strauss syndrome (allergic granulomatous angiitis), Buerger's disease thromboangiitis obliterans, necrotizing vasculitis and antineutrophil cytoplasmic antibody (ANCA) positive vasculitis (type unspecified), Henoch-Schonlein purpura, Behcet's syndrome, leukocytoclastic vasculitis	 Antiphospholipid syndrome Autoimmune hemolytic anemia Autoimmune glomerulonephritis (glomerulonephritis rapidly progres glomerulonephritis, membranopro mesangioproliferative glomerulone Autoimmune myocarditis/cardiome Autoimmune thrombocytopenia Goodpasture syndrome Idiopathic pulmonary fibrosis Pernicious anemia Raynaud's phenomenon Sarcoidosis Sjögren's syndrome Stevens-Johnson syndrome Uveitis 	ssive, membranous liferative glomerulonephritis, and ephritis)

Appendix I Infant visit windows

Visit Number	Visit Type	Lower Allowable Window	Lower Target Day	Target Day ¹	Upper Target Day	Upper Allowable Window
01.0	Screening	-5	-	-	-	+0
02.0	Enrollment/Vaccination 1	-	-	0	-	-
03.0	Follow-up		-	1	+2	-
04.0	2 Weeks Post-Vaccination	-	-4	14	+4	+7
05.0	Vaccination 2	-	-9	56	+9	+14
06.0	2 Weeks Post-Vaccination	-	-4	70	+4	+7
07.0	Vaccination 3	-21	-14	112	+14	+21
08.0	2 Weeks Post-Vaccination Primary Immunogenicity	-	-4	126	+4	+7
09.0	Vaccination 4	-28	-14	224	+14	+28
10.0	2 Weeks Post-Vaccination	-	-4	238	+4	+7
11.0	Vaccination 5	-28	-14	379	+14	+28
12.0	2 Weeks Post-Vaccination Primary Immunogenicity	-	-4	393	+4	+7
13.0	Follow-up	-	-14	516	+14	+21
14.0	Final Visit	-28	-14	743	+14	+28

¹Target dates are relative to Day 0 (Enrollment), with the exception of postvaccination visits 4.0, 6.0, 8.0, 10.0, and 12.0 which are relative to the prior vaccination visit.

Appendix J Mother visit windows

Visit Number	Visit Type	Lower Allowable Window	Lower Target Day	Target Day ¹	Upper Target Day	Upper Allowable Window
01.0	Screening	-273	-	-	-	+0
02.0	Enrollment/Infant Vaccination	-	-	0	-	-
03.0	Follow-up	-	-	1	+2	-
04.0	Follow-up	-	-4	14	+4	+7
05.0	Follow-up	-	-9	56	+9	+14
06.0	Specimen Collection	-	-4	70	+4	+7
07.0	Follow-up	-21	-14	112	+14	+21
08.0	Specimen Collection	-	-4	126	+4	+7
09.0	Follow-up	-28	-14	224	+14	+28
10.0	Specimen Collection	-	-4	238	+4	+7
11.0	Follow-up	-28	-14	379	+14	+28
12.0	Specimen Collection	-	-4	393	+4	+7
13.0	Follow-up	-	-14	516	+14	+21
14.0	Final Visit	-28	-14	743	+14	+28

¹Target dates are relative to Day 0 (Enrollment), with the exception of visits 4.0, 6.0, 8.0, 10.0, and 12.0 which are relative to the prior visit.

1 OVERVIEW

The following describes the Statistical Analysis Plan (SAP) for the analysis of immunogenicity data from HVTN **135** for Protocol Team (PT) reports for immunogenicity data, and the FSR for Immunogenicity.

2 PROTOCOL SUMMARY

2.1 Title

HVTN 135 is a phase 1 clinical trial to evaluate the safety and immunogenicity of the HIV-1 CH505 transmitted/founder gp120 adjuvanted with GLA-SE in healthy, HIV-exposed uninfected infants

2.2 Study products and routes of administration

- CH505TF gp120: CH505TF gp120 with the adjuvant GLA-SE. GLA-SE is an oil-inwater stable emulsion (SE) containing the immunological adjuvant Glucopyranosyl Lipid A (GLA). The vaccine will be administered by intramuscular (IM) injection in the thigh at 2 doses of gp120 (5 or 20 mcg) and 2 doses of adjuvant (2.5 mcg or 5 mcg).
- Placebo: Sodium Chloride for Injection, 0.9% USP, administered IM in the thigh at volumes to match the active product.

2.3 Schema

		Injection schedule in weeks				
Group	N	Week 0	Week 8	Week 16	Week 32	Week 54
Part A	•		Initia	al Safety	•	1
1	5	20 mcg CH505TF gp120 +2.5 mcg GLA-SE				
2	2	Placebo	Placebo	Placebo	Placebo	Placebo
Part B	•	•	Safety	Ramp-Up	•	•
3	2	20 mcg CH505TF gp120 +5 mcg				
4	2	GLA-SE Placebo	GLA-SE Placebo	GLA-SE Placebo	GLA-SE Placebo	GLA-SE Placebo
Part C		Immuno	genicity of CH5	05TF Recombin	nant Protein	
5	16	20 mcg CH505TF gp120 +5 mcg GLA-SE				
6	3	Placebo	Placebo	Placebo	Placebo	Placebo
7	5	5 mcg CH505TF gp120 +5 mcg GLA-SE				
8	3	Placebo	Placebo	Placebo	Placebo	Placebo
Total	38	28 vaccinees,	10 placebos	•	•	_

Notes: To ensure safety, enrollment will proceed in stages.

Groups 3 and 5 (20 mcg CH505TF and 5 mcg GLA-SE) and Groups 2, 4, 6, and 8 (placebo) will be pooled in the ultimate analyses.

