8.1 Vaccine regimen

The schedule of vaccination is shown in Section 3 and additional information is given below.

Part A

Group 1

Treatment 1 (T1): 20 mcg Stable CH505TF gp120 admixed with 2.5 mcg GLA-SE, to be administered as a 0.25 mL intramuscular (IM) injection into either thigh at Weeks 0, 8, 16, 32, and 54.

Group 2

Control 2 (C2): Placebo for 20 mcg Stable CH505TF gp120 + 2.5 mcg GLA-SE (Sodium Chloride for Injection, 0.9%) to be administered as a 0.25 mL IM injection, into either thigh at Weeks 0, 8, 16, 32, and 54.

Part B

Group 3

Treatment 3 (T3): 20 mcg Stable CH505TF gp120 admixed with 5 mcg GLA-SE, to be administered as a 0.5 mL IM injection into either thigh at Weeks 0, 8, 16, 32, and 54.

Group 4

Control 4 (C4): Placebo for 20 mcg Stable CH505TF gp120 + 5 mcg GLA-SE (Sodium Chloride for Injection, 0.9%) to be administered as a 0.5 mL IM injection, into either thigh at Weeks 0, 8, 16, 32, and 54.

Part C

Group 5

Treatment 5 (T5): 20 mcg Stable CH505TF gp120 admixed with 5 mcg GLA-SE, to be administered as a 0.5 mL IM injection into either thigh at Weeks 0, 8, 16, 32, and 54.

Group 6

Control 6 (C6): Placebo for 20 mcg Stable CH505TFgp120 + 5 mcg GLA-SE (Sodium Chloride for Injection, 0.9%) to be administered as a 0.5 mL IM injection, into either thigh at Weeks 0, 8, 16, 32, and 54.

Group 7

Treatment 7 (T7): 5 mcg Stable CH505TF gp120 admixed with 5 mcg GLA-SE, to be administered as a 0.5 mL IM injection into either thigh at Weeks 0, 8, 16, 32, and 54.

Group 8

Control 8 (C8): Placebo for 5 mcg Stable CH505TF gp120 + 5 mcg GLA-SE (Sodium Chloride for Injection, 0.9%) to be administered as a 0.5 mL IM injection, into either thigh at Weeks 0, 8, 16, 32, and 54.

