11.3 Safety reviews

11.3.1 Safety Evaluations for moving from Part A to Part B and Part B to Part C

To ensure safety, enrollment will proceed in stages. In addition to monitoring participant safety throughout the study period, the HVTN 135 PSRT will review safety data as shown in Table 11-2.

There are two planned enrollment holds and one planned safety review. An enrollment hold prevents advancement of the study to the next part but does not prevent participants from receiving further vaccinations. Part B cannot enroll until the safety data following the first vaccination in all seven infants in Part A has been reviewed (Enrollment Hold #1). Part C cannot begin enrollment until all safety data following the third vaccination in Part B has been reviewed (enrollment hold #2).

There is also a planned safety review to occur after the final infant in part B (the fourth infant) has receives the first vaccination. During this safety review, no infants in Part B will receive further vaccinations until the PSRT has reviewed all cumulative safety information.

Table 11-2 Summary of planned enrollment holds and safety reviews

Planned Holds and Reviews	Timepoint/Data Reviewed	Actions		
Planned Safety Hold #1 Enrollment in Parts B and C are on hold.	Begins after the 7 th participant receives first vaccination in Part A. Review of all cumulative safety data available for the seven participants in Part A (Groups 1 and 2) up to and	The PSRT will make a decision based on this safety data regarding the appropriateness of beginning enrollment in Part B from a safety perspective.		
	including the 2-week visit after the first vaccination.			
Planned Safety Review in Part B	Begins after the 4th participant in Part B (Groups 3 and 4) receives their first vaccination.	The PRST will make a decision based on this safety data regarding the appropriateness of continuing Part B vaccinations from a safety perspective.		
All vaccinations in Part B are on hold.	Review of all cumulative safety data available for:	vaccinations from a safety perspective.		
Enrollment in Part C is on hold.	 all participants in Part A. all four participants in Part B (Groups 3 and 4) up to and including the 2-week visit after the first vaccination. 			

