9.5 Env-specific B-cell Phenotyping (BCP)

The Env-Specific B cell Phenotyping (BCP) assay will be used to identify and characterize HIV-1 Env-specific B cells and plasmablasts induced by vaccination. The BCP analysis corresponds to

the primary objective to determine whether vaccination with CH505TF gp120 adjuvanted with GLA-SE initiates B-cell lineages potentially capable of generating a broadly neutralizing antibody response. HVTN135 study design will also allow for the comparison infant and adult immune responses to CH505TF gp120 as it mimics the design of HVTN115 that evaluated CH505TF gp120 in adult humans. The study will evaluate two dose levels of the vaccine (20 and 5 mcg) and two dose levels of the adjuvant (2.5 and 5 mcg) given at five time points over 54 weeks. The study consists of 38 total participants: 28 vaccinees and 10 placebo recipients. All vaccines as well as the placebo will be delivered via intramuscular injection (IM).

Samples from baseline (Obtained from cord blood), visit 8 and visit 12 from the maximum of 38 infants in the protocol will be assayed as part of this study.

HIV-1 Env-specific B cells induced by vaccination were identified and characterized using fluorescently-labeled recombinant Env proteins in the context of a flow cytometry panel to identify and characterize those B cells.

Total B cells are identified using doublet exclusion, lymphocyte scatter profile, a viability dye to exclude dead cells, and are negative for lineage markers: CD3, CD56 and CD14; and positive for CD19 and CD20. B cells are further gated as IgD-, then IgG+, and IgA+.

Data from Low IgD- B cells (<5000) and assay results deemed unreliable for analysis by the lab were excluded from the analysis.

To assess positivity for the detection of IgD-, IgG+, and IgA+ B cells, the 85th percentile of the proportion of cells in the subset was calculated, among all placebo recipients (C2+C4+C6+C8) for a given cell subset and visit (visits 8 and 12) and used as the threshold for defining a positive response. Positivity was not assessed for visit 1.

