10 weeks	Hexavalent (DTaP-IPV-HepB-Hib) -2
14 weeks	Rotavirus (RV) -2
	Pneumococcal conjugate (PCV) -2
	Hexavalent (DTaP-IPV-HepB-Hib) -3
6 months	Measles/Rubella (MR) -1
9 months	Pneumococcal conjugate (PCV) -3
12 months	Measles/Rubella (MR) -2

Tables will show the percent of infants with protective antibody levels or those with a detectable response and corresponding 95% confidence intervals calculated by the Wilson score test method [1], as well as summary statistics among participants with protective levels of antibodies or those with a detectable response and among all participants. Differences in the percent of infants with protective antibody levels/detectable response between vaccine and placebo groups (T1 + T3+ T5 + T7 vs. pooled placebo) will be reported alongside 95% confidence intervals for each antigen. Also, geometric mean ratios of IgG concentrations against each antigen between vaccine and placebo groups (T1 + T3+ T5 + T7 vs. pooled placebo) will be evaluated among all participants and reported alongside 95% confidence intervals.

Boxplots of concentrations of antibody will show both percent of infants with protective antibody levels/detectable responses and the distribution of IgG concentration. Participants with protective levels of antibodies/detectable responses will be indicated by dots color-coded by treatment group, and negative responses by gray triangles. Data points for each participant (if any) are connected by a grey line. Box plots based upon data from only participants with protective levels of antibodies/detectable responses are superimposed on the distributions. Alternatively, for plots including all participants, box plots based upon data from all participants are superimposed on the distributions. The mid-line of the box denotes the median and the ends of the box denote the 25th and 75th percentiles. Whiskers extend to the extreme data points that are no more than 1.5 times the interquartile range or if no value meets this criterion, to the data extremes. Scatterplots will show infant PVMA response vs. NAb response and infant PVMA response vs. BAMA IgG AUC response.

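### The PVMA comparison of all vaccinees with pooled placebo ignores Part, within which infants are randomised; stratifying by Part costs about 4% in variance with complete data

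*SAP*

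**What the plan says.** Both schemas (Protocol Table 3-1, SAP 2.3) combine the four placebo groups: "Groups 2, 4, 6, and 8 (placebo) will be pooled in the ultimate analyses". SAP 9.5 gives the totals: "The study consists of 38 total participants: 28 vaccinees and 10 placebo recipients".

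SAP 9.7 plans two vaccine-placebo estimates for each antigen at visit 12, each with a 95% confidence interval. One is the difference in the percentage of infants with a protective or detectable level. The other is "geometric mean ratios of IgG concentrations against each antigen between vaccine and placebo groups (T1 + T3+ T5 + T7 vs. pooled placebo"), estimated among all participants. This endpoint answers secondary objective 1, the effect of the study vaccine on responses to routine infant vaccines.

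Enrolment is staged. Protocol 11.3.1 says that "Part B cannot enroll until the safety data following the first vaccination in all seven infants in Part A has been reviewed", and that Part C waits for the Part B review after the third vaccination.

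Neither Randomization section (Protocol 6.2, SAP 6) names Part as a stratum, and no analysis section names it as a covariate. The nearest provision is the fallback model in SAP 8.4.1. It applies when more than 20% of participants have missing values and takes in all available baseline predictors, without naming Part.

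**The concern.** Each treatment group belongs to one Part and the Parts open in sequence, so assignment can only take place within Part. Randomisation therefore protects the within-Part contrasts. Because the allocation ratio changes from 2.5:1 to 1:1 to 3.5:1, collapsing over Part compares arms with different Part mixes. Anything that shifts antibody levels between Parts then enters the vaccine-placebo difference.

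The PVMA endpoint is a plausible place for such a shift. Its panel includes RSV, which is absent from the EPI schedule printed in the same section, so RSV antibody at month 13 cannot come from a scheduled dose. Infants in Parts A and C are also born months apart. What is at stake is the estimate of whether the adjuvanted vaccine interferes with routine immunisation.

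**Working it through.** **Inputs.** Group sizes are from SAP 2.3: Part A 5 and 2, Part B 2 and 2, Part C 16 + 5 = 21 and 3 + 3 = 6. They sum to 28 vaccinees and 10 placebos, matching SAP 9.5. The documents give no variance or power figure for the PVMA contrast, so there is nothing further to reproduce. A common within-Part variance σ² is assumed.

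**Separation in time.** By the target days in Protocol Appendix I, Part B opens at least 14 days after the last first dose in Part A. Part C opens at least 112 + 14 = 126 days after the last Part B enrolment. Parts A and C are thus at least about 14 + 126 = 140 days apart.

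**Part shares.**

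| | A | B | C |
|---|---|---|---|
| Vaccine (28) | 5/28 = 17.9% | 2/28 = 7.1% | 21/28 = 75.0% |
| Placebo (10) | 2/10 = 20% | 2/10 = 20% | 6/10 = 60% |
| Difference, points | −2.1 | −12.9 | +15.0 |

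**Bias of the crude contrast.** Bias = Σ (share difference in Part k) × (outcome shift of Part k). If Part C differs from A and B by δ, the bias is 0.15δ.
- δ = 0.5 SD gives 0.075 SD.
- δ = 1 SD gives 0.15 SD.
- The crude standard error is √0.1357 = 0.368 SD, so these are 0.20 and 0.41 standard errors.

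**Variance, complete data.**
- Crude: 1/28 + 1/10 = 0.1357σ².
- Stratified, with weights nV·nP/(nV + nP): A 10/7 = 1.429, B 4/4 = 1.000, C 126/27 = 4.667, sum 7.095. The variance is 1/7.095 = 0.1409σ².
- Ratio: 0.1409/0.1357 = 1.039, an increase of 3.9%. Allowing for the two degrees of freedom lost, the interval is about 2% wider.
- If Part C was randomised as two strata (Groups 5/6 and 7/8), which the documents do not say, the weights are 1.429 + 1.000 + 48/19 + 15/8 = 6.830. The variance is 0.1464σ², an increase of 7.9%.

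**Break-even in mean squared error.** Set (0.15δ)² = 0.14094 − 0.13571 = 0.00523. Then δ = √(0.00523/0.0225) = 0.48 SD.

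**With the planned 25% missing.** Simulating independent 25% loss gives a mean variance increase of about 7%, with a 90th percentile of 15%. The chance that a Part loses a whole arm follows directly:
- Part B: 1 − (1 − 0.25²)² = 12.1%.
- Part A: 1 − (1 − 0.25²)(1 − 0.25⁵) = 6.3%.
- Either: 1 − 0.879 × 0.937 = about 18%. That Part then drops out of the stratified contrast.

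**Groups 3 + 5 against placebo, if reported.** Shares are 0/11.1/88.9% against 20/20/60%.
- Crude: 1/18 + 1/10 = 0.1556σ².
- Stratified over Parts B and C: 1/(1.000 + 96/22) = 1/5.364 = 0.1864σ², an increase of 20%.
- An unstratified 18 against 8 gives 1/18 + 1/8 = 0.1806σ², an increase of 16%. It also widens the Part B imbalance from 8.9 points (11.1% against 20%) to 13.9 points (11.1% against 25%). The sensitivity analysis should therefore be stratified.

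**The case against.** The case for leaving the plan alone has substance.

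- **No Part effect is documented.** The bias is conditional on a shift that nobody has sized. Below about 0.48 SD the crude estimate is the better one in mean squared error. This stands, and is why the crude estimate should be kept.
- **The calendar spread is limited.** Planned duration is 32 months in total against 24.5 months per participant, leaving about 7.5 months for enrolment and holds. The PVMA analysis is restricted to infants with all relevant EPI doses, and the site gives delayed ones. The documents do not say that assay batches follow Part. This weakens the mechanisms but does not remove them. The dose restriction does nothing for RSV.
- **The strata are sparse.** Part B is 2 against 2, and 3.9% is a complete-data figure. This also stands.
- **Pooling is pre-specified and placebo comparisons are described as descriptive** (Protocol 4.4.6). Pooled displays are unaffected by the proposal, but SAP 9.7 attaches confidence intervals to a between-arm difference.

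A reader might also infer that injection volume leaks into this contrast and could be removed for 4%. Part A placebo is indeed half the volume used in Parts B and C: "Placebo for 20 mcg Stable CH505TF gp120 + 2.5 mcg GLA-SE (Sodium Chloride for Injection, 0.9%) to be administered as a 0.25 mL IM injection". But in the all-vaccine contrast the 0.25 mL shares are 17.9% and 20%, so even a 1 SD volume effect moves the estimate by only 0.02 SD. The volume imbalance (0% against 20%) belongs to Groups 3 + 5 against placebo. There stratifying costs 20%, and the SAP lists no table for that comparison.

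**Conclusion.** The point holds for the two PVMA estimates in SAP 9.7. They compare 28 vaccinees with 10 placebos across sequentially enrolled Parts with unequal allocation, and Part is left out. The possible bias is 0.075 to 0.15 SD for an assumed Part C shift of 0.5 to 1 SD. Removing it costs 3.9% in variance with complete data and about 7% on average with 25% missing. These figures rest on a common variance, Parts A and B being alike, and independent missingness. No claim about volume is made for this contrast.

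A reader might extend this to every vaccine-placebo comparison in the trial. The documents do not support that. The prioritised analysis of immunogenicity response rates is a one-sample comparison with zero (SAP 8.4.1), adverse events are not formally tested (SAP 8.3.2), and the neutralisation comparisons listed in SAP 9.6 are among vaccine arms only. Nor do the documents show that a Part effect exists. This is a low-severity improvement, not a fault in the primary analysis.

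**What to change.** In SAP 9.7 and 9.7.1:

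1. Estimate each geometric mean ratio from a model for log concentration with treatment and Part as factors.
2. Report a Part-stratified difference in percentages, for example Mantel-Haenszel weighted, with an interval method suited to sparse strata named in advance.
3. Keep the pooled displays and show the crude estimate beside the stratified one. State what happens when a Part has an empty arm.
4. If Groups 3 + 5 are compared with placebo, add a sensitivity analysis against the eight Part B and C placebos, stratified by Part.

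The work is one extra factor, one stratified estimate and at most one further table, with no new data or design change. The statistical cost is the added variance: about 4% to 7% for the PVMA contrast and about 20% for the sensitivity analysis. In addition, Part B may contribute nothing if either of its arms is lost.
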